#### Open-Label Extension of the Halt cardiomyOPathy progrEssion in Duchenne (HOPE-Duchenne) Trial

# **REVISION HISTORY**

Version	Date	Summary of Revision(s)
1.0	26 March 2019	New Document

# LIST OF ABBREVIATIONS AND DEFINITION OF TERMS

Term	Explanation	Term	Explanation		
6MWT	6-Minute Walk Test	LV	Left Ventricle / Left Ventricular		
AE	Adverse Event	LVEDV	Left Ventricular End-Diastolic Volume		
ALT	Alanine Aminotransferase	LVEF	Left Ventricular Ejection Fraction		
AST	Aspartate Aminotransferase	LVESV	Left Ventricular End-Systolic Volume		
ATC	Anatomic Therapeutic Chemical	M cells	Million cells		
BMI	Body Mass Index	MedDRA	Medical Dictionary for Regulatory Activities		
BUN	Blood Urea Nitrogen	MEP	Mean Expiratory Pressure		
BSA	Body Surface Area	MFI	Mean Fluorescence Intensity		
CBC	Complete Blood Count	MIP	Mean Inspiratory Pressure		
CDC	Cardiosphere-Derived Cells	mL	Milliliter		
CEC	Clinical Events Committee	MRI	Magnetic Resonance Image		
CI	Confidence Interval	OLE	Open-Label Extension		
CK-MB	Creatine kinase MB Isoenzyme	PCF	Peak Cough Flow		
DMD	Duchenne Muscular Dystrophy	PEF	Peak Expiratory Flow		
DSA	Donor-Specific Antibody	PFT	Pulmonary Function Test		
DSMB	Data Safety Monitoring Board	PI	Primary Investigator		
ECG	Electrocardiogram	РР	Per Protocol		
EOS	End-of-Study	РТ	Preferred Term		
FEV 1	Forced Expiratory Volume in 1 Second	PUL	Performance of the Upper Limb		
FVC	Force Vital Capacity	QTc	Corrected QT		
HLA	Human Leukocyte Antigen	RBC	Red Blood Cell		
IFR	Inspiratory Flow Reserve	SAE	Serious Adverse Event		
IP	Investigational Product	SD	Standard Deviation		
ITT	Intent-to-Treat	SOC	System Organ Class		
IV	Intravenous	SOP	Standard Operating Procedures		
LS	Least Square	SpO 2	Peripheral Capillary Hemoglobin Oxygen Saturation		

Term	Explanation
SAP	Statistical Analysis Plan
TEAE	Treatment-Emergent Adverse Events
TLF	Tables, Listings and Figures

Term	Explanation
SVC	Slow Vital Capacity
WBC	White Blood Cell
WHODrug Global	World Health Organization Drug Global Dictionary

# **1 STUDY OVERVIEW**

Duchenne muscular dystrophy (DMD) is a severe, X-linked, progressive disease affecting approximately one in 3,600 to 9,200 male births caused by mutations in the dystrophin gene resulting in the absence of or non-functional dystrophin protein.

DMD occurs in early childhood, with degeneration occurring progressively in the skeletal musculature and ultimately in the heart and respiratory muscles, resulting in premature death. Progressive weakness and muscle atrophy caused by degenerating muscle fibers begins in the lower extremities and pelvis before spreading into the upper extremities. Other symptoms include loss of some reflexes, a waddling gait, frequent falls, difficulty when rising from a sitting or lying position or when climbing stairs, changes to overall posture, and impaired breathing. Many children precipitously lose the ability to run or jump. The atrophied muscles, in particular the calf muscles, and less commonly, muscles in the buttocks, shoulders, and arms, may be enlarged by an accumulation of fat and connective tissue, causing them to look larger and healthier than they actually are ("pseudohypertrophy"). Bone thinning and scoliosis are common. Ultimately, a wheelchair becomes necessary, in most cases between 12 to 15 years of age.

No pharmacologic or biological therapies proven to stop or reverse the progression of DMD have been approved in the US. Disease management consists primarily of preventive measures as well as active interventions to address the primary and secondary aspects of the disorder.

The proposed open-label extension (OLE) trial will enroll subjects randomized to the Usual Care Treatment Group in the HOPE-Duchenne trial (CAP-1002-DMD-01) and who completed the 12-month follow-up period. All subjects enrolled in the OLE will receive CAP-1002.

CAP-1002 is intended to be used as a therapeutic to improve the morbidities associated with DMD and thus improve or prevent decline in muscle function through its composite immune-modulatory, anti-fibrotic, and regenerative mechanisms of action. Preliminary clinical evidence from the HOPE-Duchenne trial in subjects with cardiomyopathy secondary to DMD suggests that CAP-1002 can have systemic effects; including benefits on skeletal function (as assessed by mid-level PUL) compared to usual care control subjects. This clinical evidence suggests that CAP-1002 has the potential to address unmet medical needs for patients with DMD.

# 2 STUDY OBJECTIVES AND ENDPOINTS

## 2.1 Study Objectives

#### 2.1.1 Primary

To provide CAP-1002 to subjects who were randomized to the Usual Care Treatment Group of the HOPE-Duchenne trial and completed the 12-month follow-up period.

#### 2.1.2 Secondary

To explore the safety and efficacy of intravenous administration of CAP-1002 with repeat dosing at Month 3.

# 2.2 Study Endpoints

#### 2.2.1 Primary Safety Endpoint

The *primary safety endpoints* include the incidence of the following from baseline through the 6-month timepoint:

- Acute respiratory decompensation within 2 hours following Investigational Product (IP) administration
- Hypersensitivity reaction
  - Hypersensitivity reaction is defined as a clinical syndrome including, but not limited to, fever, leukocytosis, or rash with onset  $\leq 2$  hours post infusion and lasting < 24 hours, in the absence of clinical signs of concomitant infection.
- All-cause mortality
- Serious adverse events (SAEs)
- Treatment-emergent adverse events (TEAEs) related to IP or administration procedure
- Immune sensitization syndrome
  - Immune sensitization syndrome shall be defined as:

(a) clinical signs and symptoms consistent with systemic inflammation (e.g., fever, leukocytosis, rash, or arthralgia) with onset  $\geq 24$  hours post infusion and the absence of clinical signs of concomitant infection,

AND

(b) elevation of anti-human leukocyte antigen (HLA) antibodies against the donor cells (i.e., DSAs), detected  $\leq$  30 days following onset of syndrome, of

- (i)  $\geq$  2000 mean fluorescent intensity (MFI) if baseline MFI  $\leq$  1000, or
- (ii)  $\geq$  2 times baseline otherwise

#### 2.2.2 Exploratory Efficacy Endpoints

The *exploratory endpoints* include the change from baseline to each assessment timepoint for the following assessments:

- All subjects
  - Mid-level (elbow) dimension of the Performance of the Upper Limb (PUL) 1.2
  - Mid- and distal-level (elbow) dimension of the PUL 1.2
  - High-level (shoulder) dimension of the PUL 1.2
  - Left ventricular structure and function, as assessed by cardiac MRI, including regional systolic left ventricular wall thickening, ejection fraction, end-diastolic volume, end-systolic volume, stroke volume, regional wall thickness, and circumferential strain
  - Slow vital capacity (SVC), forced expiratory volume in one second (FEV1), forced vital capacity (FVC), peak expiratory flow (PEF), maximum inspiratory pressure (MIP), maximum expiratory pressure (MEP), peak cough flow (PCF), and inspiratory flow reserve (IFR)
- Ambulatory subjects only
  - 6-Minute Walk Test (6MWT)

# **3 STUDY DESIGN**

This Phase 2, multi-center, open label extension trial will provide CAP-1002 to subjects who were randomized to the Usual Care Treatment Group and completed 12 months of follow-up in the HOPE-Duchenne trial. The trial will assess the safety of CAP-1002, administered as two IV infusions, each separated by 3 months. All subjects will undergo targeted tests and procedures within 30 days prior to first infusion, unless otherwise stated, to confirm eligibility based on protocol inclusion and exclusion criteria.

Eligible subjects will undergo baseline safety and efficacy assessments (APPENDIX B) prior to the first infusion of CAP-1002. Administration of CAP-1002 (Day 1) should occur within a maximum of 14 days following confirmation of eligibility; if a delay of more than 14 days between enrollment and CAP-1002 administration is unavoidable, a conversation between the Investigator and Medical Monitor should occur to determine the need for repeat assessments prior to infusion. For the purposes of this trial, enrollment is defined as the time consent is signed.

All intravenous infusions will be conducted in an outpatient setting at the investigative site on Day 1 and at Month 3. Subjects will be observed in the outpatient setting for at least two hours post infusion and then discharged the same day if medically cleared by the site Investigator.

A safety phone call will be performed 14 days ( $\pm 3$  days) after each CAP-1002 infusion, and if clinically indicated, an unscheduled in-person visit will be performed at the investigative site with targeted assessments based on presentation of signs and symptoms.

Blood samples will be collected at Week 4 and Month 4 ( $\pm$ 7 days, respectively) for DSA testing and safety laboratory assessments. Collection will occur either at the investigative site or remotely at a designated central laboratory patient service center.

Subsequent trial visits at the investigative site will occur at Months 3 and 6 ( $\pm$ 14 days, respectively). Subjects will complete safety and efficacy assessments at each of these visits and prior to CAP-1002 administration in the case of the Month 3 trial visit.

A schematic of the study design is displayed in Figure 1.

#### Figure 1 Trial Design

Safety Outcome Measures: AEs, PE, VS, WT & HT, ECG, CBC w/ diff, Hgb, HCT & plts, basic metabolic panel, comprehensive hepatic panel, CK, CK-MB, cTnI, DSA Efficacy Outcome Measures: cMRI, PUL 1.2, 6MWT, core lab standardized PFTs (SVC, spirometry, MIP & MEP, PCF and IFR)

# **3.1 Data Safety Monitoring Board**

The Data Safety Monitoring Board (DSMB) will act in a senior advisory capacity to Capricor regarding data and safety matters throughout the duration of the trial. The objectives, roles and responsibilities of the DSMB, as well as the format and frequency of their meetings are documented in the DSMB charter.

## 4 GENERAL STRATEGIES FOR DATA PRESENTATION

Data with qualifiers (e.g. "<") will be listed with the qualifier but summarized without the qualifier. Subject data listings will include data collected for all subjects. Listings will be sorted by treatment, site, subject number, nominal visit, date and time (as applicable), unless otherwise indicated.

Categorical analyses will be summarized using counts and percentages. Percentages will be based on the number of subjects in the analysis set for whom data are available, unless otherwise specified. Continuous variables, including change from baseline, will be summarized using descriptive statistics (n, mean, standard deviation [SD], median, minimum, maximum).

All analyses will be performed using SAS v 9.3 or higher (SAS Institute, Inc, Cary, North Carolina, USA). Validation and quality control of the tables, listings and figures (TLFs) will follow the appropriate Innovative Analytics standard operating procedures (SOPs).

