## 7.3. Number of Subjects

Up to 10 subjects will be enrolled.

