## 4.4 Analysis Populations

The following analysis populations will be defined.

- Intent-to-Treat (ITT) Population: The Intent-to-Treat (ITT) population will be defined as all subjects who meet the enrollment criteria and are enrolled in the study.
- Safety Population: The Safety population will be defined as all subjects who receive any amount of IP.
- Per Protocol (PP) Population: The PP population will include subjects who have no protocol deviations/violations that could significantly impact the completeness, accuracy and/or reliability of the trial data. The list of subjects in the per protocol population will be compiled prior to database lock.

A summary of the number and percentage of subjects in each analysis population will be provided. A listing of subject assignment into each analysis population will also be displayed.

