# 6.1 PUL Scale

All subjects, regardless of ambulatory status, will complete testing the 1.2 module in the same preferred arm. Observed values and changes from baseline, mid- and distal-levels combined and for each dimension (high-level, shoulder; mid-level, elbow; distal-level, wrist and hand) separately, will be summarized. The 95% confidence intervals (CI) for the mean estimates will also be displayed.

The observed values will be displayed in subject listings.

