# 7 SAFETY ANALYSES

Listings and summaries of the safety parameters will be done for the Safety population. An overall summary table will be presented that summarizes the primary safety endpoints. Safety parameters are described below.

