# 7.1 Adverse Events

Adverse events will be coded using the Medical Dictionary for Regulatory Activities (MedDRA) coding system (Version 21.0). Potential primary safety endpoints, described in Section 2.2.1, will be adjudicated by an independent Clinical Events Committee (CEC).

The following AEs are defined as treatment-emergent AEs (TEAEs):

- AEs occurring after the initiation of the IV catheter placement for the initial dose of IP; or
- AEs with a completely missing start date, or similarly, AEs that started the same month and year as IP administration but with missing start day.

Subject listings of all adverse events as reported will be provided. A separate listing will be done for TEAEs as adjudicated by the CEC. All summary tables will be reported using as adjudicated by the CEC.

An overall summary table will be presented by treatment group that summarizes subject with the following:

- Any TEAEs
- TEAEs by maximum severity
- TEAEs and serious TEAEs by greatest degree of relationship to IP or IP administration
- TEAEs and serious TEAEs by greatest degree of relationship to IP only
- TEAEs and serious TEAEs by greatest degree of relationship to IP administration only
- Serious TEAEs
- TEAEs leading to study discontinuation, and
- TEAEs leading to death

In addition, TEAEs will be summarized overall by system organ class and preferred term and by severity and by relationship to the IP and IP administration procedure.

Deaths, AEs that resulted in study discontinuation, serious adverse events (SAEs), serious TEAEs and AEs within 24 hours of IP administration will be listed and summarized.

Summaries of 'related' TEAEs, will include TEAEs with a reported relationship to IP and/or IP administration of "Probable" or "Possible". Adverse events will be displayed by MedDRA System Organ Class and Preferred Terms, with subjects who have the same adverse event counted only once for that event and with subjects who have more than one adverse event within a System Organ Class counted only once in that System Organ Class. The numbers and percentages of subjects reporting an event as well as the number of events that were reported will be displayed.

Frequency tables will be ordered by decreasing percentage in the SOCs, then alphabetically. Within each SOC, PTs will be ordered by decreasing percentage then alphabetically.

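### The six primary safety incidences are reported as counts and percentages with no interval, so a 0% among at most 10 subjects would appear without its exact 95% upper limit of at least about 31%

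*SAP*

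**What the plan says.** **Endpoints.** SAP 2.2.1, like Protocol 7.2.1, says the primary safety endpoints "include the incidence of the following": acute respiratory decompensation, hypersensitivity reaction, death from any cause, serious adverse events, related treatment-emergent adverse events, and immune sensitization syndrome. Each can be read as yes or no for a subject.

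**How they are summarized.** SAP 4 gives the general rule, "Categorical analyses will be summarized using counts and percentages", and the denominator: "Percentages will be based on the number of subjects in the analysis set for whom data are available, unless otherwise specified". SAP 7 adds: "An overall summary table will be presented that summarizes the primary safety endpoints". SAP 7.1 adds, for adverse events: "The numbers and percentages of subjects reporting an event as well as the number of events that were reported will be displayed". Protocol 14.4.1 likewise speaks of incidences and percentages, and adds relatedness and severity for adjudicated events. Neither document provides an interval for any proportion.

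**Where intervals are planned.** For upper limb performance, SAP 6.1 says: "The 95% confidence intervals (CI) for the mean estimates will also be displayed". SAP 6.2 (pulmonary function) and 6.3 (cardiac MRI) say the same. SAP 6.4 (six-minute walk) plans observed values and changes only. Protocol 14.6 ties its 95% intervals to means of continuous measures.

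**Size and purpose.** Protocol 7.3 says "Up to 10 subjects will be enrolled", and Protocol 14.2 repeats that cap with no statement of precision. The primary objective is to provide the product to former usual-care subjects (Protocol 6.1, SAP 2.1.1). Safety and efficacy are explored as secondary objectives (Protocol 6.2, SAP 2.1.2). Protocol 14.1 and 14.6.1 disclaim formal hypotheses.

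**The concern.** Three groups of exploratory outcomes carry a statement of precision, while the endpoints that the plan labels primary carry none, and the documents do not explain the difference. With at most 10 subjects a percentage alone says little. The likeliest awkward result is a zero for one of the rarer events, such as immune sensitization syndrome, and a printed 0% does not show how high a rate the data still allow.

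What is at stake is how the primary safety table is read. Protocol 5.4 already describes the safety profile as favorable, and Protocol 5.6.3 argues that repeat dosing should carry low immune risk. A row of zeros without limits could be taken as firmer support for those statements than 10 subjects can give.

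**Working it through.** The plan gives no power, precision or detectable-rate figure, so there is no stated number to reproduce. The check asks what an interval would show.

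**Inputs**
- Number of subjects: at most 10 (Protocol 7.3 and 14.2). The Synopsis, under its number of subjects, says approximately 10; I use the cap of 10.
- Denominator: subjects with data in the Safety population, defined in SAP 4.4: "The Safety population will be defined as all subjects who receive any amount of IP". It can fall below 10 if fewer are enrolled or infused.
- Level: two-sided 95%. This is my assumption for proportions, chosen to match the level planned for the means.

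**No events in n subjects.** The lower limit is 0. The upper limit solves (1 − p)^n = 0.025, so p = 1 − 0.025^(1/n).

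| Result | Upper limit |
|---|---|
| 0/10 | 1 − 0.025^(1/10) = 30.8% |
| 0/9 | 1 − 0.025^(1/9) = 33.6% |
| 0/8 | 1 − 0.025^(1/8) = 36.9% |

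The limit rises as n falls. With at most 10 subjects, about 31% is therefore the smallest value that this upper limit can take.

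**x events in 10 subjects.** The limits are the beta quantiles B(0.025; x, 11 − x) and B(0.975; x + 1, 10 − x).
- 1/10: 0.3% to 44.5%
- 2/10: 2.5% to 55.6%

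**Check by direct probability.** The chance of seeing no event in 10 subjects is (1 − p)^10:
- true rate 10%: 0.90^10 = 0.349
- true rate 20%: 0.80^10 = 0.107
- true rate 30%: 0.70^10 = 0.028

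A true rate of 1 in 5 would give a clean zero about one time in nine.

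**Sensitivity to method, 0/10**
- one-sided exact 95%: 1 − 0.05^(1/10) = 25.9%
- rule of three: 3/10 = 30.0%
- Wilson, two-sided: 3.8415/(10 + 3.8415) = 27.8%
- Jeffreys, two-sided: 21.7%

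The figure moves with the method, but every choice leaves a rate above 1 in 5 compatible with zero events.

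**The case against.** The strongest reply is that the plan is openly descriptive. It tests nothing, sets no event rate to exclude, and makes safety a secondary, exploratory aim. In a trial this small, safety is judged mainly case by case: by-subject listings, summaries of deaths and serious events, independent adjudication, and a monitoring board. The split between intervals for continuous means and counts for events also follows data type and need not be neglect of safety. Finally, anyone with the count and the denominator can compute the interval.

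Most of that is true, and it limits the point to a reporting improvement. It does not remove the point. An interval is not a test, and the plan itself shows intervals for exploratory means under the same no-hypothesis framework. Readers could equally rebuild those mean intervals from the n, mean and SD that SAP 4 reports, yet the SAP displays them. Protocol 14.6 asks that methods suit the data type, which permits an interval for a proportion but does not commit to one.

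Two technical reservations also stand. Acute respiratory decompensation and hypersensitivity are defined within 2 hours of an infusion, and two infusions are planned, so a per-subject interval does not give a per-infusion risk. The subjects also come from a closed pool, the completers of one arm of an earlier trial, so the wider population to which a limit applies is not well defined. Both are reasons to label the interval carefully.

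**Conclusion.** The point holds as a modest gap in precision reporting. The six primary safety incidences have no interval, while the upper limb, pulmonary and cardiac MRI means do. An observed 0% would be shown without a two-sided exact 95% upper limit that is at least about 31%. That figure rests on no events, at most 10 subjects in the denominator, the exact method, and subjects treated as independent with one yes-or-no outcome each.

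A reader might infer more than the documents support:
- That the trial exists to establish the safety of repeat infusion and cannot do so. The primary objective is to provide the product; safety is only explored.
- That every efficacy outcome gets an interval. SAP 6.4 plans none for the six-minute walk.
- That 31% is a fixed result or an estimate of risk. It is the most favorable value of an upper limit under the assumptions above.
- That the plan treats a zero as absence of risk. Nothing in either document says so; over-reading is a possibility for readers, not a planned conclusion.
- That a calculation is wrong. None is stated.

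No planned estimate or analysis population changes.

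**What to change.** In SAP 7, state that the overall summary table will show, for each of the six primary safety endpoints, the number and percentage of Safety-population subjects with the event and the two-sided exact (Clopper-Pearson) 95% confidence interval for that proportion. Add a footnote that the intervals are descriptive and per subject, not per infusion. A separate rule to repeat the upper limit beside every zero is unnecessary, because the column already shows it.

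The cost is one extra column in one table, with no new data and no change to trial conduct. The downside is that zero-event results will look less reassuring. The choice should be written down before results are known, so that it cannot appear to depend on them.

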## 4.1 Treatment Group

The treatment group to be presented will be composed of those subjects who receive CAP-1002.

# 4.2 Study Day

The day of the first IP administration is defined as Day 1. All other study days will be labeled relative to Day 1. Thus, the study day for a particular event date on or after Day 1 is calculated as: (*Date of event – Date of first IP administration + 1*). An event that occurs prior to Day 1 is calculated as: (*Date of event – Date of IP administration)*.

The duration of an event will be calculated as *(Event end date – Event start date + 1)*. Day 0 will not be used.

The baseline value for each subject is the last non-missing value obtained prior to the time of the first IP administration on Day 1.

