#### **Objectives**:

*Primary*: To provide CAP-1002 to subjects who were randomized to the Usual Care Treatment Group of the HOPE-Duchenne trial and completed 12 months of follow-up.

*Secondary*: To explore the safety and efficacy of intravenous administration of CAP-1002 with repeat dose at Month 3.

**Methodology:** This Phase 2, multi-center, open label extension trial will provide CAP-1002 to subjects that were randomized to the Usual Care Treatment Group of the HOPE-Duchenne trial (CAP-1002-DMD-01) and explore the safety of two intravenous administrations of CAP-1002, each separated by three months. Subjects will undergo targeted tests and procedures during a 30-day screening period to determine eligibility based on protocol inclusion and exclusion criteria.

Eligible subjects will undergo baseline safety and efficacy assessments on Day 1 prior to their first infusion of CAP-1002. Administration of CAP-1002 (Day 1) should occur within a maximum of 14 days following confirmation of eligibility; if a delay of more than 14 days between enrollment and IP administration is unavoidable, a conversation between the Investigator and Medical Monitor should occur to determine the need for repeat assessments prior to infusion.

All CAP-1002 infusions will be conducted in an outpatient setting at the investigative site on Day 1 and Month 3. Subjects will be observed in the outpatient setting for at least two hours post infusion and then discharged the same day if medically cleared by the site Investigator.

A safety phone call will be performed 14 days ( $\pm 3$  days) after each CAP-1002 infusion, and if clinically indicated, an unscheduled in-person visit will be performed at the investigative site with targeted assessments based on presentation of signs and symptoms.

Blood samples will be collected before each CAP-1002 administration (Day 1 and Month 3), after each CAP-1002 infusion (Week 4 and Month 4) and at Month 6, unless otherwise indicated, for donor specific antibody (DSA) testing and routine serum chemistries, hematology and cardiac enzymes. HLA

typing will occur before the first CAP-1002 administration on Day 1. Collection will occur either at the investigative site or remotely at a designated central laboratory patient service center.

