Trial visits at the investigative site will occur at Months 3 and 6 ( $\pm$ 14 days, respectively). Subjects will complete safety and efficacy assessments prior to CAP-1002 administration at the Month 3 trial visit.

The *primary safety endpoints* include the incidence of the following from baseline through the 6-month timepoint:

- Acute respiratory decompensation within 2 hours following IP administration
- Hypersensitivity reaction
  - Hypersensitivity reaction is defined as a clinical syndrome including, but not limited to, fever, leukocytosis, or rash with onset  $\leq 2$  hours post infusion and lasting < 24 hours, in the absence of clinical signs of concomitant infection.
- All-cause mortality
- Serious adverse events
- Treatment-emergent adverse events related to IP or administration procedure
- Immune sensitization syndrome
  - Immune sensitization syndrome shall be defined as: (a) clinical signs and symptoms consistent with systemic inflammation (e.g., fever, leukocytosis, rash, or arthralgia) with onset ≥ 24 hours post infusion and the absence of clinical signs of concomitant infection, AND (b) elevation of anti-human leukocyte antigen (HLA) antibodies against the donor cells (i.e., DSAs), detected ≤ 30 days following onset of syndrome, of (i) ≥ 2000 mean fluorescent intensity (MFI) if baseline MFI ≤ 1000, or (ii) ≥ 2 times baseline otherwise

The *exploratory endpoints* include the change from baseline to each assessment timepoint for the following assessments:

- All subjects
  - Mid-level (elbow) dimension of the Performance of Upper Limb (PUL) 1.2
  - Mid- and distal-level (elbow) dimension of the PUL 1.2
  - High-level (shoulder) dimension of the PUL 1.2
  - Left ventricular structure and function as assessed by cardiac MRI including regional systolic left ventricular wall thickening ejection fraction, end-diastolic volume, endsystolic volume, stroke volume, regional wall thickness, and circumferential strain
  - Slow vital capacity (SVC), forced expiratory volume in one second (FEV1), forced vital capacity (FVC), peak expiratory flow (PEF), maximum inspiratory pressure (MIP), maximum expiratory pressure (MEP), peak cough flow (PCF), and inspiratory flow reserve (IFR)
- Ambulatory subjects only

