#### 5.6.3. Repeat Administrations

The other element of safety relevant for the open label extension trial and related to the planned dosing regimen, is the potential for an immune response to the allogeneic product, planned for repeated administrations. Several lines of evidence suggest that repeat administration of CAP-1002 should have low immunotoxicity risk in humans.

In fact, equivalent

primary (i.e., after a first dose) and secondary (i.e. after a second dose) efficacy benefits (i.e., improvements in LVEF) were observed using allogeneic and syngeneic CDCs in this study. Furthermore, there was no evidence of an increased cellular or humoral immune memory response using allogenic compared to syngeneic CDCs. These collective data suggest that repeat administration of CAP-1002 should be reasonably safe in humans.

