#### 13.2.1.3. Expected Adverse Events

As CAP-1002 is comprised of allogeneic cells, immunologic reactions to the product are a possible adverse event. However, to date, no significant immune system adverse events have been identified with any likelihood of relationship to CAP-1002.

There is some risk of developing transient DSA with the CAP-1002 allogeneic product. All subjects will be monitored during the trial for immune sensitization as outlined in Table 3.

Other risks of the infusion procedure include those risks that are possible with the intravenous administration. These include risks related to infection, bleeding, pain, and bruising and/or hematoma at the vascular access site(s).

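### After Infusion 2 the DSA limb of immune sensitization syndrome is still judged against Day 1, so the met/not-met flag alone does not show whether the repeat dose raised DSA

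*SAP*

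**What the plan says.** The SAP has one definition of baseline, in section 4.2: "The baseline value for each subject is the last non-missing value obtained prior to the time of the first IP administration on Day 1". Neither document gives a separate reference value for the second infusion.

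Immune sensitization syndrome is defined in the protocol synopsis, protocol 7.2.1 and SAP 2.2.1. Limb (a) is clinical: signs of systemic inflammation starting at least 24 hours post infusion, without infection. It does not say which infusion, so it covers both. Limb (b) is a DSA elevation, detected within 30 days of onset, "of (i) ≥ 2000 mean fluorescent intensity (MFI) if baseline MFI ≤ 1000, or (ii) ≥ 2 times baseline otherwise". The endpoint counts incidence from baseline to 6 months.

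DSA is drawn on Day 1 and at Week 4, Month 3, Month 4 and Month 6, and the Month 3 sample is to be taken before Infusion 2 (protocol Table 3 and footnote 6; SAP Appendix B). SAP 5.8 lists MFI for each subject at each visit. It promises an analysis of DSA in the context of the syndrome if one occurs, without naming a comparison.

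The SAP's secondary objective (2.1.2) is "To explore the safety and efficacy of intravenous administration of CAP-1002 with repeat dosing at Month 3". Protocol 5.6.3 identifies as a relevant safety element "the potential for an immune response to the allogeneic product, planned for repeated administrations".

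**The concern.** The trial gives a second dose of an allogeneic product and sets out to explore the safety of doing so. A natural question after Infusion 2 is whether DSA rose in response to it. Limb (b) answers a different question: whether DSA is raised relative to the value before any exposure. The two answers can differ whenever DSA moved between Day 1 and Month 3.

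The documents leave room for such movement. Protocol 13.2.1.3 states: "There is some risk of developing transient DSA with the CAP-1002 allogeneic product". Protocol 10.2 says subjects are dosed whatever their pre-existing DSA, so a Day 1 MFI above 1000 is not excluded.

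The more consequential direction is the missed rise. A subject with a compatible clinical syndrome and a several-fold DSA increase after the second dose could be counted as having no immune sensitization event. SAP 5.8 would not necessarily recover the case, because its DSA analysis depends on an occurrence of the syndrome, and a case that fails limb (b) is not one.

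**Working it through.** The plan states no figure for this endpoint and no sample size calculation, so there is nothing to reproduce. The check applies the rule as written to assumed MFI values.

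**Rule.** For a reference value x, the limb (b) threshold is T(x) = 2000 if x ≤ 1000, and T(x) = 2x if x > 1000. The plan uses x = Day 1 MFI. The alternative uses x = the last MFI before Infusion 2 (here, Month 3).

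**Assumed paths** (illustrative; the documents give no DSA distribution):

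| Day 1 / Month 3 pre-infusion / Month 4 | Month 4 ÷ Month 3 | Day 1 threshold: result | Pre-Infusion 2 threshold: result |
|---|---|---|---|
| 500 / 4000 / 2100 | 0.525 (48% fall) | 2000: met | 8000: not met |
| 500 / 2500 / 2500 | 1.00 | 2000: met | 5000: not met |
| 1500 / 3200 / 3200 | 1.00 | 3000: met | 6400: not met |
| 500 / 1500 / 2100 | 1.40 | 2000: met | 3000: not met |
| 3000 / 1500 / 5900 | 3.93 | 6000: not met | 3000: met |
| 1500 / 500 / 2500 | 5.00 | 3000: not met | 2000: met |
| 1500 / 900 / 2900 | 3.22 | 3000: not met | 2000: met |
| 500 / 500 / 2500 | 5.00 | 2000: met | 2000: met |
| 500 / 2500 / 6000 | 2.40 | 2000: met | 5000: met |

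In the first three rows the limb is met with no rise after Infusion 2; each was already at its Day 1 threshold before that infusion. In rows five to seven a rise of 3.2- to 5-fold is not counted.

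**Size of a rise that can be missed.** Let the pre-Infusion 2 value be r times a Day 1 value above 1000. The Day 1 threshold is 2 × Day 1 = (2/r) × the pre-Infusion 2 value, so any rise of less than 2/r-fold is not counted. For r = 0.75 this is 2/0.75 = 2.7-fold; for r = 0.5 it is 2/0.5 = 4-fold. The 3000/1500/5900 path lies close to the cut-off, but the result does not depend on that: every Month 4 value from 3000 up to just under 6000 meets the pre-Infusion 2 threshold and fails the Day 1 threshold.

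**When an either-reference rule changes the result.** Counting the limb as met on either reference means using the smaller of the two thresholds. T(x) is flat at 2000 up to x = 1000 and increases after that. The pre-Infusion 2 threshold is therefore lower than the Day 1 threshold only if Day 1 MFI was above 1000 and the pre-Infusion 2 value was lower than Day 1. For a subject with Day 1 MFI of 1000 or less, classification never changes: 500/4000/2100 stays met and gains only the label that the Day 1 reference alone was met.

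**Weight of one subject.** With at most 10 subjects, 1/10 = 10 percentage points, and more if fewer are treated. This applies only to subjects whose classification changes.

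**The case against.** A reader might infer that the Day 1 baseline is simply wrong. The documents do not support that. The endpoint is incidence over the whole period from baseline to 6 months, and a pre-exposure reference is coherent for cumulative sensitization over a two-dose course. On that view, counting 500/4000/2100 is legitimate: the subject became sensitized, was re-exposed, and had a non-infectious inflammatory syndrome while DSA was still raised. This stands. Such a case is not a false positive; it just cannot be credited to the second dose.

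A reader might also infer that the trial cannot tell whether the repeat dose raised DSA. That is too strong. The Month 3 pre-infusion value is collected and listed, and with at most 10 subjects the change to Month 4 can be read off for each. The Clinical Events Committee adjudicates potential primary safety endpoints, with immunology consultants as needed, and the clinical event may still appear as a related TEAE or an SAE. What is missing is a pre-specified comparison in the endpoint rule. Protocol 14.4.4 (summary by donor) and SAP 5.8 do not supply one.

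The missed-rise path is also narrow. It needs a Day 1 MFI above 1000, a fall by Month 3, a later rise short of twice Day 1, and limb (a). The protocol speaks only of some risk of transient DSA, which does not show that values stay at 2000 or more until Month 3. This limits the likely frequency but does not remove the gap.

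Finally, applying SAP 4.2 to a committee-adjudicated definition is an inference, since the committee's charter is not among the documents. It is nevertheless the only baseline definition the documents give.

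**Conclusion.** The point holds for the met/not-met flag as defined. After Infusion 2, limb (b) reports cumulative change from Day 1 and does not by itself show whether the repeat dose raised DSA. Of the two consequences, only the missed rise changes who is counted; the other is a matter of attribution.

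The conclusion rests on SAP 4.2 governing the word baseline in the syndrome definition. The MFI paths are assumptions that show the mechanism; how often DSA moves in these ways cannot be derived from the documents. The practical weight is modest: the analysis is descriptive with no formal hypotheses (protocol 14.1), the trial is small, and DSA alone never triggers the endpoint. The change is still worth making, because it bears directly on the repeat-dose safety objective and uses data already planned.

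**What to change.** In protocol 7.2.1 (and the synopsis, which repeats the definition) and SAP 2.2.1, keep the Day 1 reference for the cumulative endpoint. Add that, for syndromes with onset after Infusion 2, thresholds (i) and (ii) are also applied against the last MFI before Infusion 2; that limb (b) is met if either reference is met; and that the report states which one was met. In SAP 5.8, name both comparisons as the planned DSA analysis.

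The label should be read with care. Met on Day 1 only means no threshold-size rise from the pre-Infusion 2 value; it does not exclude a smaller rise, as in 500/1500/2100.

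The cost is a few sentences and one extra column. No visit, blood draw or subject is added. The downside is that a few more cases may qualify, all with Day 1 MFI above 1000 and a lower value before Infusion 2.
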